We anticipate that groups that are enrolled in the regular aerobic exercise will show maintenance or enhancement of potential gains from the other interventions. This group (n=20) will show maintained or better upper extremity performance in conjunction with increased levels of interhemispheric inhibition as compared to 9 month assessments and the no-intervention group. The no-intervention group will still show improvement as compared to their enrollment assessments.

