*TMS Analysis.* Six measures will be computed and analyzed from TMS acquisitions: Right FDI MEP size, right FDI MEP latency, recruitment curves (RC), ipsilateral silent period (iSP), interhemispheric inhibition at 10ms (IHI10) and 40ms (IHI40). The size of left FDI MEP evoked by TMS will be measured from peak-to-peak between TMS stimulation (first peak) and subsequent muscle response (second peak). The latency of MEPs will be measured from the onset of the stimulus presentation to the onset of the MEP. Recruitment curves will be evaluated based on slope generated from linear regression. Onset and end latency of the iSP will be taken at the initial and final intersections of the averaged signal with baseline indicating 80% of the background EMG level; the duration of EMG suppression between these two points will be computed. For each of the stimulation intensities, IHI will be expressed by  $(1 - \text{mean conditioned MEP} / \text{mean unconditioned MEP}) \times 100\%$ . Accordingly, IHI = 0%, IHI = 100%, and IHI < 0% will indicate no inhibition, complete inhibition, and interhemispheric facilitation, respectively. For within subjects comparison, repeated measures ANOVA with subsequent repeated measures pairwise t-tests will be generated. Group comparisons of TMS measures will be analyzed by between-subjects ANOVA and subsequent t-test pairwise comparisons. For all test, p-values < 0.05, corrected for multiple comparisons where applicable, will be considered statistically significant.

*BDNF Evaluation.* Fasting whole blood will be collected, by a certified phlebotomist, via venipuncture or peripheral venous line into pre-cooled plasma EDTA tubes and serum separator tubes (~40 ml per visit). Following collection, tubes will be transferred in sealed biohazard bags and in according with blood borne pathogens training standards to the Molecular Biology Lab (4A 178/4A 167) of the Atlanta VAMC Center of Excellence.

Plasma volume will be measured using methods described by Dill and Costill. Lactate will be measured by the Accusport Lactate Analyzer (Roche Molecular Biochemicals, Mannheim, Germany). Serum samples will be allowed to clot for 30 minutes before centrifugation at 1000g for 15 minutes. Plasma samples will undergo centrifugation within 30 minutes of collection at 1000g for 15 minutes at 2-8°C. Plasma aliquots will be separated and will then undergo an additional centrifugation "Super-

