### **Specific Aim 3) To determine if role of exercise duration in maintaining or enhancing motor performance and levels of interhemispheric inhibition.**

*Introduction:* Behavioral interventions (motor strength and coordination) have been shown to be effective in improving upper extremity motor performance in older adults (Christou, 2011; Engler et al., 2011), however the duration of these gains appear to be short-lived (Toraman, 2004; Ivey et al., 2000). After as little as a few weeks of detraining, motor strength and coordination in the upper extremity rapidly begins to return to pre-intervention levels (Carvalho et al., 2009; Toraman, 2005; Toraman & Ayceman, 2005;). Evidence from exercise interventions assessing gait and locomotion have shown that exercise programs over a longer term (>6 months) are associated with improved proprioception, fewer falls and better balance (Arnold et al., 2008). However, the comparison of outcomes of upper extremity function in elderly adults respective of exercise duration remains largely unexplored. In addition to comparing the effects of short-term exercise (3 months) versus behavioral training (3 months) on upper extremity function, the current proposal will evaluate if a longer-term (6 months) exercise program

can maintain or enhance upper extremity function and associated levels of interhemispheric inhibition. Further, we will inquire as to how the long-term exercise program has affected the general quality of life in our sample.

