## 7. Statistical Analysis

**Statistical Analysis for Specific Aim 1.** We will model each of the outcome measures in Aim 1 (upper extremity) jointly using a mixed linear model to determine whether the mean responses of the groups are significantly different across the time points. We expect that modeling the outcomes jointly, using subject as a random factor, will allow for some gains in power. Our fixed factors will be time, treatment group and their interaction. This model will enable us to estimate the overall effects of time and treatment, and most importantly, how the effects of treatment differ with time.

**Statistical Analysis for Specific Aim 2.** For each of the outcome measures in Aim 2 (changes in fMRI and TMS activity during unimanual tasks) we will use a mixed linear model to determine whether the mean responses of the groups are significantly different across the time points. Our fixed factors will be time, treatment group and their interaction. This model will enable us to estimate the overall effects of time and treatment, and most importantly, how the effects of treatment differ with time.

**Statistical Analysis for Specific Aim 3.** For each of the outcome measures in Aim 3 we will use a mixed linear model to determine whether the mean responses of the groups are significantly different across the time points. Our fixed factors will be time, treatment group and their interaction. This model will enable us to estimate the overall effects of time and treatment, and most importantly, how the effects of treatment differ with time. Level of interhemispheric inhibition will be characterized by proportion of ipsilateral motor cortex recruited during fMRI tasks, ipsilateral silent period in TMS, and level of diminution of MEP size in the interhemispheric inhibition protocol in paired-pulse TMS.

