**Power Analysis and Sample Size.** We powered this study on the previous cross-sectional studies assessing interhemispheric communication and motor performance. These studies had large effect sizes (1.33 to 1.67) as aerobic activity was related to ipsilateral motor cortical activity. As the proposed work is an intervention, we have applied a conservative estimate of these effects based on previous work with behavioral performance training over a similar timeframe (Kornatz et al., 2005) and those in the neuroimaging literature (Erickson et al., 2011). Further, data from our ongoing CDA-1 pilot study has shown a somewhat linear relationship between VO2max and levels of interhemispheric inhibition. While this data does not provide enough information to enable us to estimate a required sample size under the mixed model that will be used in the final analysis, we can conservatively estimate the sample size assuming a two-sample t-test would be performed on the post-pre differences for each group. Under this simpler model, a sample size of 20 per group will give us an approximate effect size of .83 for the fMRI and TMS measures. While this effect sizes is relatively large, we will have more power under the mixed model that we actually will use to analyze the data. Equally important, from the standpoint of our sample size, is that the data gathered on the other outcome measures would be invaluable in fully powering future study. Lastly, based on the retention rates in previous exercise studies we anticipate a 20 percent

drop-out rate among groups. As such, we will plan to enroll 24 per group to reach the needed sample size of 20 per group.

The research staff will use REDCap issued through the Atlanta Veterans Health Care System. Only deidentified data will be entered into REDCap by VA credentialed research personnel to run data analysis.

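### Aim 3 predicts that performance is maintained from 9 months, but the planned difference test cannot support that, so a non-significant loss could be reported as maintenance

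*Combined protocol and SAP*

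**What the plan says.** Section 4 (Objectives, Aim 3) anticipates that participants in regular aerobic exercise "will show maintenance or enhancement of potential gains from the other interventions". It then states the prediction: "This group (n=20) will show maintained or better upper extremity performance", together with increased interhemispheric inhibition, "as compared to 9 month assessments and the no-intervention group". So there are two comparators: the group's own level at 9 months, and a concurrent arm that does not exercise.

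The introduction to Specific Aim 3 in section 5 puts the same question, namely whether a six-month program "can maintain or enhance upper extremity function and associated levels of interhemispheric inhibition". It explains that gains from behavioral training fade within weeks once training stops.

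For the analysis of Aim 3, section 7 says "we will use a mixed linear model to determine whether the mean responses of the groups are significantly different across the time points". The fixed factors are time, treatment group and their interaction, and the model is also meant to estimate these effects. The documents do not define 'maintained' or set a margin. They give no equivalence, non-inferiority or confidence-interval rule, and they do not single out the change from the 9-month to the final assessment as a contrast.

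**The concern.** A test of difference can show that performance fell or that it rose. When it shows neither, the data may be compatible with no change, with a small gain or with a material loss. Only the interval tells these apart. 'Maintained' is a claim that any loss is small, so it needs a stated size of loss and evidence that excludes it.

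This matters here because loss of gains is what the protocol's own rationale expects without continued exercise. If the exercise arm lost part of its 9-month gain and the test missed it, the report could say that performance was maintained, and nothing in the plan would rule that wording out. The sample size offers no protection: section 7 sizes the study on a difference in fMRI and TMS measures, not on motor performance or on maintenance.

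**Working it through.** **Inputs.** From the documents: 20 people in the exercise group (section 4); 20 per group, a two-sample t-test on change scores and an effect size of 0.83 (section 7, Power Analysis and Sample Size); a significance level of 0.05, stated only under TMS Analysis in section 5 ("For all test, p-values < 0.05, corrected for multiple comparisons where applicable, will be considered statistically significant"). Assumed: two-sided testing, 80% power where a power is needed, and losses in units of the SD of change. Section 7 gives no alpha, sidedness, power or SD.

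**The plan's own figure.** For a two-sample t-test with 20 per group, two-sided 0.05 and 80% power, the detectable effect is 0.91 (normal approximation: (1.960 + 0.842) × √(2/20) = 0.89). At 0.83 the power is 72.5%. Because alpha and power are not stated, whether 0.83 reproduces cannot be settled. The present point does not depend on it.

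**Chance that a true within-group loss is non-significant.** The statistic T follows a noncentral t distribution with 19 df and noncentrality d × √20, where d is the true loss in SDs of change. The probability wanted is P(|T| < t(0.975, 19)), that is P(|T| < 2.093).

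| True loss d | d × √20 | P(non-significant) |
|---|---|---|
| 0.2 | 0.89 | 86% |
| 0.3 | 1.34 | 75% |
| 0.4 | 1.79 | 60% |
| 0.5 | 2.24 | 44% |

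**Interval width.** The 95% half-width for the within-group change is 2.093 / √20 = 0.47 SD, so an observed loss just under 0.47 SD would be non-significant. For the between-arm difference in change, with 20 per arm, it is t(0.975, 38) × √(2/20) = 2.024 × 0.316 = 0.64 SD.

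**What a margin would require.** Suppose the true change is zero and maintenance is shown when the 95% interval for the exercise arm excludes a loss of m (a one-sided 0.025 one-sample t-test). The margins below are an assumed range.

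| Margin m (SD of change) | Power with n = 20 | n for 80% power |
|---|---|---|
| 0.2 | 13% | 199 |
| 0.3 | 25% | 90 |
| 0.4 | 40% | 52 |
| 0.5 | 56% | 34 |

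The smallest margin with 80% power at n = 20 is 0.66 SD. At one-sided 0.05 it would be 0.58 SD.

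**The case against.** The case for leaving the plan alone has several parts.

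- **The between-arm question is properly covered.** One comparator is a concurrent arm that stops exercising, and the time-by-group interaction tests exercise against it. This stands. However, doing better than a declining arm shows that exercise slowed the loss; it does not show that the 9-month level was kept, and section 4 names that comparison too.
- **Estimation is already promised.** Section 7 says the model will estimate how treatment effects vary over time. This also stands, but the 9-month-to-final contrast and its interval are not named, and an estimate without a rule does not define 'maintained'.
- **The prediction is a joint one.** It pairs motor performance with increased inhibition, so a non-significant motor loss alone would not fulfil all of it. True, but the motor half can still be reported separately.
- **The illustration is not the planned test.** Section 7 expects that "we will have more power under the mixed model that we actually will use to analyze the data". The mixed model may indeed be somewhat more precise than a one-sample t-test. Extra precision does not supply a margin. The loss sizes are assumptions, and at 0.5 SD a miss is already less likely than not.
- **Motor outcomes did not drive the sample size.** Section 7 presents the other outcome measures as useful for planning a later study. That argues for a modest claim, not for leaving the claim undefined.

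A reader might go further and infer that the plan will count a non-significant loss as maintenance. The documents do not support this: section 4 states an expectation, and no section states such a decision rule. A reader might also infer that Aim 3 as a whole cannot be tested. That is wrong too, because improvement, superiority over no intervention and increased inhibition are ordinary difference hypotheses.

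**Conclusion.** The point holds for one part of Aim 3: the word 'maintained', measured against 9 months within the exercise arm. The planned difference test cannot establish it and no other criterion is given, so a non-significant loss could be reported as maintenance.

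The absence of a criterion is a matter of reading the text and needs no assumption. Its size is illustrative. It rests on 20 completers, simple t-tests at two-sided 0.05 and losses expressed in SDs of change, because the documents give no SD and no expected gain. On that basis, losses of 0.3 to 0.4 SD would more often be missed than found. The remedy is a cheap improvement to the analysis text; the design is not at fault.

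**What to change.** In section 7, under the Aim 3 analysis:

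1. Name the between-arm difference in change from the 9-month to the final assessment, with its 95% interval, as the main contrast.
2. Report the exercise arm's own change over the same period with its 95% interval, and state that non-significance will not be read as maintenance.
3. Allow the word 'maintained' only if the confidence limit on the worsening side excludes a fixed margin for that outcome. That is the upper limit for timed tasks (nine-hole pegboard, coin rotation, Jebsen Taylor) and the lower limit for count or strength scores (Purdue pegboard, finger tapping, pinch and grip).
4. Justify each margin before the data are seen, and do not derive it from the gain observed in the trial. Such a gain is itself uncertain and shares the 9-month measurement with the change being judged.
5. Otherwise give the estimate and interval and describe the result as no significant change detected.

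The cost is SAP wording; no visits, data or participants are added. The downside is a harder claim: with 20 people only a margin of about 0.66 SD of change has 80% power. If so wide a margin cannot be defended, maintenance should be presented as estimation only.

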## 5. Study Design and Methods:

**Specific Aim 1) To determine the relative effectiveness of a behavioral motor training regimen versus an aerobic exercise regimen respective of upper extremity motor performance.**

*Introduction.* A critical aspect for rehabilitation of motor pathology is the understanding of the neural mechanisms at work in the healthy brain. Sedentary aging is associated with changes in interhemispheric communication within the brain that likely denote a loss of interhemispheric inhibition ([name] et al., 2011; [name] et al., 2009; Riecker et al., 2006; Fling et al, 2011; Bernard & Seidler, 2011; Fling & Seidler, in press). There is evidence that these changes are associated with declines in motor performance of the upper extremity including dexterity, reaction time and psychomotor performance (Langan et al., 2010; Fling & Seidler, in press; [name], unpublished CDA1 data). Data from previous work ([name] et al., 2011) and preliminary data from a recently completed project ([name] et al., 2012) shows that aerobic activity may serve to mitigate losses of interhemispheric inhibition and improve motor performance. It is unknown whether aerobic activity can reduce loss of interhemispheric inhibition. In the current project, we test the hypothesis that an aerobic activity regimen can be effective in mitigating losses of interhemispheric inhibition and improve motor performance.

*Research Design.* The proposed study will examine 40 older, sedentary Veterans from the greater Atlanta area. Participants will be randomly assigned to one of two 15-month intervention conditions involving aerobic fitness training and behavioral training. The study is a reversal design in which both groups are assessed pre-treatment with both fMRI and TMS measures, as well as behavioral measures at study enrollment. As part of the design, both groups will undergo a 3-month waiting period during which they will engage in an organized stretching routine with no aerobic exercise component. After this waiting period, the participants again undergo behavioral, fMRI and TMS assessments. At this point, the participants will be assigned to either a behavioral treatment group involving a motor coordination protocol previously shown to improve upper extremity motor performance in older adults (Christou et al, 2011) or a supervised aerobic training group at the Atlanta VA Medical Center. The design of the study is depicted in the in Figure 6 below. The primary outcomes of this aim are changes in fMRI and TMS measures of interhemispheric communication and motor performance tests.

The 12-week behavioral training component of the study is an adaptation of a motor training program previously shown increase dexterity, coordination and decrease motor output variability in older adults (Kornatz et al., 2005; Christou et al., 2011). Training involves the regular engagement in contraction and relaxation of the first dorsal interosseous (FDI) muscle response recorded via surface EMG. Training session will occur three times per week consistent with the exercise intervention. The training begins with a 1 week familiarization period over three experimental sessions. In the familiarization sessions, subjects will receive written and oral descriptions of the project, watch a visual demonstration of the protocol, and are allowed initial practice trials of the experimental task. The experimental task is an adaptation of an anisometric abduction-adduction task of the index finger (Kornatz et al., 2005). Participants will lift and lower the same load identified by the recruitment threshold by using abduction-adduction movements of the index finger that are produced with shortening and lengthening contractions of the first dorsal interosseus (finger bending with a weight). Participants will attempt to match index finger displacement to a template shown on a computer monitor; they will be required to produce slow, constant-velocity ( $1.7^\circ/\text{s}$ ) abduction-adduction movements over a  $10^\circ$  range of motion. Each subject will raise the load during 6 s of abduction (shortening contraction) and lowered the load during 6 s of adduction (lengthening contraction). Participants will repeat this movement five times for an exercise trial. We will carefully monitor the hand to ensure movement is limited to abduction of the index finger about the metacarpophalangeal joint. The weekly experimental sessions include 5 weeks of light-load training (50% of maximum), and an additional 6 weeks of heavy-load training (75% of maximum). This design will allow each subject to serve as their own control in addition to allowing for assessment of group differences at the end of the project. Four motor training activities will be made in these sessions: recruitment threshold, determination of the minimal weight load that had to be supported by an isometric contraction of the FDI for the isolated motor unit to discharge action potentials repetitively; anisometric task, shortening and lengthening contractions of the first dorsal interosseus muscle to lift and lower a light inertial load; and one repetition maximum load, i.e.- identification of the maximal load that could be lifted by a shortening contraction of the first dorsal interosseus muscle. The discharge of motor units will be recorded during the anisometric task. Each experimental session will last 45 minutes.

After the each group has completed the first component of the study, behavioral and neuroimaging (fMRI/TMS) assessments will be completed. The groups will then switch from the exercise intervention to the behavioral or vice-versa, depending on initial assignment. The interventions will proceed as previously described within these groups for another 12-week timeframe after which imaging and behavioral assessments will again be taken to test for effect of training type and effect of reversal.

## Fitness Assessments:

Fitness level will be assessed using four measurements:

- **Physical Activity Inventory:** During phone screening we will ask the participant about their current aerobic activity.
- **Direct Assessment:** Following written consent, the participant will be asked to complete a direct measure of aerobic fitness using a submaximal assessment commonly conducted to estimate aerobic capacity.
- **Daily Log:** During the study, the participant will complete the Physical Activity Inventory to log their daily exercise activity.

The direct fitness assessment is to be completed at the VA Atlanta Center of Excellence Aerobic Fitness Testing Laboratory. The direct fitness assessment will consist of a sub-maximal testing protocol performed with trained research staff following ACSM (American College of Sports Medicine) testing guidelines and under the direction of an exercise physiologist. Participants will perform a sub-maximal exercise test on a cycle ergometer. We will adhere to the YMCA sub-maximal test protocol. This sub-maximal test will be used to estimate the participant's maximal oxygen uptake ( $VO_2\text{max}$ ). This test uses an "extrapolation" method in which heart rate workload values are obtained at 2-4 points and extrapolated to predict workload at the estimated maximum heart rate (MHR) (e.g.  $220 - \text{age}$ ).  $VO_2\text{max}$  is then calculated from the predicted maximum workload. Participants will be asked to ride a stationary bicycle for 4 three-minute stages. The first stage will be a warm-up at 50 revolutions per minute (RPM) at a power level of 25 watts. During all testing stages, heart rate will be continuously monitored and will not exceed 85% of age-predicted maximum heart rate. For the analysis, average heart rate during the final 30 seconds of the 2nd and 3rd minutes will be plotted against workload. Three minute trial workloads, shown in Table 1 below will be chosen based on the participants' heart rate at the end of the warm-up period. The fourth 3-minute stage will be a cool down period added to the end of the test. Participants will be allowed to stop the test at anytime for any reason and will be instructed to inform the researcher if they feel faint, dizzy, short of breath during the test, at which time the researcher will terminate the testing session.

	< 80 bpm*	80-90 bpm*	90-100 bpm*	> 100 bpm*
Stage 1	125 watts	100 watts	75 watts	50 watts
Stage 2	150 watts	125 watts	100 watts	75 watts
* beats per minute				

Immediately prior to and following the fitness test, subjects will have their heart rate and blood pressure (BP) evaluated. Individuals with a resting heart rate above 120 beats per minute, a systolic BP above 180 or a diastolic BP above 100 will not be permitted to perform the test. Heart rate and blood pressure will also be monitored throughout the assessment. Physician's clearance, for those 40 years of age or older, will be obtained from the potential subject's physician or nurse prior to conducting the fitness test with the subject's oral permission. All lab personnel present during the fitness test will be CPR certified and trained in emergency contact procedures (i.e. – VA Code Blue).

